non-steroid inflammatory drug (NSAID), metoclopramide, pantoprazole and if they underwent a surgical procedure with intermediate risk for complications, they also receive tramadol or opioids.

In addition to standard care as delineated above, patients in the intervention group (remote monitoring after discharge) will have the monitoring application installed on their personal smartphone. Once they are back home, they can start recording pain and nausea and may ask questions about their recovery within the application. Once a day patients receive a push notification to record pain and nausea. The application is operational up to 7 days post discharge. After this period the application is disconnected from the Thuismeten (Luscii) © server.

In case of recording unbearable pain and nausea or asking a question and being in need for help or assistance, an anaesthesia medical assistant will contact these patients during office hours from 08:00 to 16:30 by using the applications' messaging service or by telephone. First the medical assistant will perform an initial triage of the patients in need, subsequently pain and nausea reports and additional questions that appear as an alert in the electronic back office systems of Thuismeten (Luscii) © will be addressed. The alerts are set to the in-app question 'do you want something to be done about your pain or nausea?' or an increase of 3 points numerical rating scale (NRS) for pain and additional questions asked in the apps messaging service. During triage, the medical assistant will follow a protocolled workflow to assess actions to be taken (APPENDIX II triage workflow, in Dutch). If contacting the patient by telephone is necessary, the medical assistant will use a call script to assess patients' pain, nausea and physical status (APPENDIX III, call script, in Dutch). The medical assistant will often give appropriate feedback or advice via message or telephone. In case of a possible medical alert or a necessary medication adjustment, the medical assistant will consult the anaesthetist, trainee nurse specialist or physician assistant responsible for remote postoperative pain care.

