#### ii. Secondary study parameters/endpoints (if applicable)

Quality of recovery measured with the quality of recovery questionnaire-15 (QoR-15) (16, 24) at post discharge day at post discharge day 1, 4 and 7.

Postoperative Pain: Experienced postoperative pain (POP) measured with (in-app) NRS for Pain (25) (combined with 11 faces scale) measured at day 1, 4 and 7 post discharge.

Post discharge nausea and vomiting: Experienced post discharge nausea and vomiting (PDNV) measured with the Myles' PDNV assessment scale (21) between intervention and non-intervention group. Measured at day 1, 4 and 7 post discharge.

Medication Dosage and Use: the total dosage of administered analgesics will be assessed during hospital stay and recorded in the medical record. The total dosage of administered analgesics at home after discharge will be assessed by asking patients to indicate which pain medication they have been using. Measured at day 1, 4 and 7 post discharge.

The number of contacts with the hospital, general practitioner or emergency department. All types of contacts (e.g. physically, e-mail, telephone) will be assessed by reviewing the PDMS for registered contacts and by asking the patients to indicate the number of contacts.

Measured at day 1, 4 and 7 post discharge.

The number of surgical complications assessed according to the Clavien Dindo classification of surgical complications (26, 27) will be assessed by reviewing the PDMS and by asking the patients to indicate the number of complications. Measured at day 1, 4 and 7 post discharge.

The number of readmissions. A readmission is defined as an admission to hospital or emergency department for medical care or observation regarding their surgical intervention. Readmissions will be assessed by reviewing the PDMS and by asking the patient to indicate the number of readmissions. Measured at day 1, 4 and 7 post discharge.

Satisfaction: Patients' satisfaction with the provided care will be assessed using a 1-item self-created VAS scale ('not at all to very much', 0-10 range). Satisfaction will be measured at day 1, 4 and 7 post discharge.

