General evaluations regarding provided care after discharge: Patients' evaluations of their experienced care during the 7 day discharge period are measured using two items. i) How likely is it that the patient would recommend this hospital to other day care surgery patients (using an adapted item from the CQ index (0-10 'would definitely not recommend' to 'would definitely recommend') (28, 29). ii) Their overall rating of the quality of care provided by the hospital during the 7 day discharge period, using an item from the CQ index (0-10 scale, 'very poor care' to extremely good care') (28, 29). Both items will be measured at discharge day 1, 4 and 7.

The quality, experiences and communication regarding remote monitoring with this application will be assessed in one by one semi structured interviews. The perceptions of 20 participants are considered satisfactory or when data saturation is reached (REF). Prior to the interview, participants receive general information concerning the topics and informed consent was requested from the interviewee to allow for audio recording of the interview. See for interview topics (f1\_Interview Topics\_version\_1\_11\_2021-). Furthermore, interviews are conducted by telephone or online through Skype, Zoom or FaceTime due to COVID-19 measures.

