### b. Secondary study parameter(s)

Postoperative pain on post discharge day 1, 4 and 7: Mean, Standard Deviation, Mixed effects linear regression models will be conducted to investigate the effect of the smartphone app on postoperative pain over the first week post discharge as a function of the randomization assignment (i.e. intervention vs control), time (i.e. measurements before surgery, and at day 1, 4 and 7 post discharge), and their interaction term. Random effects, i.e. random intercept, will be fitted per individual to account for clustering effects

Post discharge Nausea and Vomiting (PDNV) on post discharge day 1, 4 and 7: Mean, Standard Deviation and Mixed effects linear regression models will be conducted to investigate the effect of the smartphone app on PDNV over the first week post discharge as a function of the randomization assignment (i.e. intervention vs control), time (i.e. measurements before surgery, and at day 1, 4 and 7 post discharge), and their interaction

term. Random effects, i.e. random intercept, will be fitted per individual to account for clustering effects

Medication Dosage and usage measured in morphine equivalents on post discharge day 1, 4 and 7: Mean, Standard Deviation and Mixed effects linear regression models will be conducted to investigate the effect of the smartphone app on medication dosage and usage over the first week post discharge as a function of the randomization assignment (i.e. intervention vs control), time (i.e. measurements before surgery, and at day 1, 4 and 7 post discharge), and their interaction term. Random effects, i.e. random intercept, will be fitted per individual to account for clustering effects

Difference in the number contacts with the hospital, general practitioner or emergency department (on day 7 post discharge): Mean and Standard Deviation and two sample-t-test (in case of non-normally distributed data we will report on medians and interquartile ranges and differences will be tested using the Mann-Whitney U test)

Difference in the number of surgical complications assessed according to the Clavien Dindo classification of surgical complications (on day 7 post discharge): Mean, Standard Deviation and two sample-t-test (in case of not normally distributed data we will use the Mann-Whitney U test)

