Difference in the number of readmissions emergency department (on day 7 post discharge): Mean, Standard Deviation and two sample-t-test (in case of not normally distributed data we will use the Mann-Whitney U test)

Satisfaction (on day 7 post discharge): Median, Interquartile Range and  $\chi^2$  tests for equal proportion.

General evaluations regarding provided care after discharge (on day 7 post discharge): Median, Interquartile Range and  $\chi^2$  tests for equal proportion.

Experienced quality of communication: Data collection and analysis progression were discussed during regular meetings with researchers. A thematic framework will be used to analyze the qualitative data. First, the audio recordings of the interviews will be transcribed verbatim in Dutch. After familiarization with the data, the transcripts are coded. After coding, overarching themes and patterns are identified and labelled within each concept.

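### Three 0-10 care ratings are summarised by median and IQR but tested by chi-squared for proportions that the plan never defines, so the same data can give different verdicts

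*Combined protocol and SAP*

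**What the plan says.** Section 7.a.ii defines three ratings of care as secondary endpoints:

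- satisfaction, a "1-item self-created VAS scale ('not at all to very much', 0-10 range";
- likelihood of recommending the hospital, "0-10 'would definitely not recommend' to 'would definitely recommend";
- overall quality of care, "0-10 scale, 'very poor care' to extremely good care".

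Section 9.b gives the analysis. For satisfaction it is "Satisfaction (on day 7 post discharge): Median, Interquartile Range and" chi-squared "tests for equal proportion". For the other two it is "General evaluations regarding provided care after discharge (on day 7 post discharge): Median, Interquartile Range and" the same chi-squared test. Neither entry lists categories, names a cut-point, or says that all score levels are to be compared.

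The neighbouring entries in Section 9.b treat non-normal outcomes differently. For the number of contacts with care providers, for example, "differences will be tested using the Mann-Whitney U test" when the data are not normal.

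**The concern.** A test of equal proportions needs categories. A median and IQR treat the rating as an ordered score. A chi-squared test on all levels ignores the order, and a dichotomy would normally be summarised by a count and percentage, which the plan does not ask for. Three readings are open:

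1. all score levels in one table;
2. a cut at an unstated value;
3. a split at the pooled median. This fits the median summary best, but with many tied scores it still needs a rule for scores equal to the median.

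Two analysts following the plan could therefore report different verdicts. The trial is non-blinded, and nothing fixes the choice before the data are exported for analysis. If the app shifts ratings across the whole scale, the chi-squared readings also lose power against a rank test.

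The stake is limited to secondary endpoints. The ratings plausibly represent the aftercare endpoint named in the Summary, though the plan does not say so, and Section 2.c does not list them among the objectives.

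**Working it through.** **Sample size used.** The sample size section gives a QoR-15 difference of 8.0, SD 19.1, two-sided alpha 0.05 and 80% power. The noncentral t calculation gives 90.45, so 91 per arm with 80.2% power, as stated. Allowing for 20% dropout, 91 / 0.8 = 113.75, so 114 per arm and 228 in total, close to the planned 230. The checks below therefore use 91 evaluable patients per arm and 230 / 2 = 115. The plan gives no figure for the ratings themselves.

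**One data set, several verdicts.** Assumed counts for scores 0 to 10:

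- control: 0, 0, 1, 1, 2, 4, 7, 15, 26, 19, 16 (median 8)
- app: 0, 0, 0, 1, 1, 2, 4, 10, 23, 24, 26 (median 9)

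For a 2x2 table with cells a, b, c, d, chi-squared = N(ad - bc)² / (product of the four margins), without continuity correction. At the cut of 9 or above: 182 × (35×41 - 56×50)² / (91×91×85×97) = 4.97.

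| Reading | Control v app, of 91 | Chi-squared | p |
|---|---|---|---|
| All levels | full table | 6.96 on 8 df | 0.54 |
| 7 or above | 76 v 83 | 2.44 | 0.118 |
| 8 or above | 61 v 73 | 4.07 | 0.044 |
| 9 or above | 35 v 50 | 4.97 | 0.026 |
| Above pooled median (8) | 35 v 50 | 4.97 | 0.026 |
| At or above pooled median | 61 v 73 | 4.07 | 0.044 |

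Mann-Whitney gives U = 5006.5 and p = 0.013. The probability of superiority is 5006.5 / (91×91) = 0.605, 95% CI 0.52 to 0.68 (DeLong).

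A second constructed data set, with median 8 and IQR 7 to 9 in both arms, behaves the same way: 0.42 for all levels, 0.100 at 7, 0.030 at 8 and at 9, and 0.011 for Mann-Whitney.

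**Simulation, whole-scale shift.** The assumed control percentages for scores 0 to 10 are 0.5, 0.5, 1, 1.5, 2, 4, 7.5, 16, 29, 21 and 17 (mean 7.8, SD 1.8). The effect is proportional odds with odds ratio 2.0, over 10,000 trials at two-sided 5%.

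| Power | 91 per arm | 115 per arm |
|---|---|---|
| All levels | 34% | 46% |
| Cut at 7 / 8 / 9 | 34% / 53% / 61% | 42% / 63% / 76% |
| Above / at or above pooled median | 60% / 54% | 74% / 65% |
| Mann-Whitney | 73% | 84% |

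At 91 per arm, five readings (all levels, the three cuts, above the median) did not all give the same verdict in 63% of trials, and in 14% with no true effect. A different assumed distribution (rounded normal, shifts of 0.6 to 0.7 points, seven readings) gave 65% to 67% disagreement and 69% to 72% power for Mann-Whitney.

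**Simulation, effect confined to part of the scale, 91 per arm.**

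- 70% of scores of 6 or below move to 7: all levels 44%, cut at 7 75%, Mann-Whitney 7%.
- 18 percentage points move from 8 to 9: all levels 70%, cut at 9 67%, Mann-Whitney 19%.

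**Type I error.** With no effect, rejection is 3% for all levels, 5% to 6% for a fixed cut or median split, and 5% for Mann-Whitney.

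**The case against.** The ambiguity itself is hard to dispute. The case against concerns its size and the remedy.

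- **The disagreement rate is conditional.** The distribution, the cuts and the odds ratio of 2.0 are all assumed. With a pooled median of 8, splitting above the median is the same as cutting at 9, so the five readings overlap. The 63% is not the chance that two analysts differ. This stands. At odds ratio 1.5 the rate falls to about 41% and Mann-Whitney power to about 35%, though that is still the highest of the tests.
- **The all-levels table is an unlikely choice.** About half its cells have expected counts below 5. That is fair, but the cuts alone still straddle 5% (0.118 against 0.044 and 0.026). Within the median-split reading, both tie rules give p below 0.05 in this example.
- **Mann-Whitney is not uniformly better.** This also stands. Staff contact follows particular triggers ("The alerts are set to the in-app question 'do you want something to be done about your pain or nausea", or a rise in pain score), so an effect on only part of the scale is conceivable. A stated cut-point would remove the ambiguity too, but it would discard information and would not match the median summary.
- **A grouping might exist in the endpoint questionnaire or data management plan.** Neither is in the supplied text, so this cannot be excluded. The analysis section should state it in any case.
- **Multiple imputation is planned (Section 9.d).** The probability of superiority has an estimate and a standard error, so it can be pooled across imputations.

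**Conclusion.** The concern holds. The plan assigns a test of proportions to three ordered 0-10 ratings without defining the proportions, and the worked data show that permissible readings fall on both sides of 5%. That such conflicts can occur needs no assumption about the true score distribution. How often they occur, and how much power is lost, rests on assumed whole-number scores and an assumed effect. If the satisfaction VAS is recorded in finer steps, the all-levels reading becomes less workable still.

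The reach is limited. Any single categorisation fixed in advance keeps its type I error near 5%, and the primary QoR-15 conclusion does not change. The correction should be made before database lock, but it does not threaten the trial's main result.

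**What to change.** In Section 9.b, replace the chi-squared tests for the three ratings with text such as: *Satisfaction, likelihood of recommending and overall care rating (0-10): median and IQR per arm; arms compared on day 7 with the Mann-Whitney U test, reporting the probability of superiority with its 95% CI.* The probability of superiority is U divided by the product of the two arm sizes. Under multiple imputation, its estimate and standard error can be pooled.

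If a proportion is also wanted, state its cut-point in the plan before database lock and label it supportive. This covers the main drawback of the rank test, its low sensitivity to an effect confined to one part of the scale.

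Day 7 is the plan's own time point for these tests and is kept, although the ratings are also collected on days 1 and 4. The change needs the same data and the same sample size; only the wording of Section 9.b changes.

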### **c. Cleaning and locking of the database**

The database will be locked as soon as all data are entered, and all discrepant or missing data are resolved – or if all efforts are employed and we consider that, the remaining issues cannot be fixed. At this step, the data will be reviewed before database locking. After that, the study database will be locked and exported for statistical analysis. At this stage, permission for access to the database will be removed for all investigators, and the database will be archived.

**d. Missing data**

No or minimal losses to follow-up for the primary and secondary outcomes are anticipated. Missing data will be accounted for with multiple imputation techniques.

**e. Interim analysis (if applicable)**

Not applicable

## 10. ETHICAL CONSIDERATIONS

### a. Regulation statement

The study will be conducted according to the principles of the Declaration of Helsinki as stated in the current version of Fortaleza, Brazil 2013, in accordance with the Medical Research Involving Human Subjects Act (WMO) and comply with Good Clinical Practice (GCP) Guidelines and all applicable national (for example WMO for the Netherlands) and international regulatory requirements and general data protection regulations (GDPR).

### b. Recruitment and consent

Patients will be recruited at the anaesthesiology outpatient clinic. Patients will be informed verbally by local researchers and by a patient information letter. The patient will be given sufficient time to consider their decision and to discuss the decision with their relatives or the independent expert.

### c. Objection by minors or incapacitated subjects (if applicable)

Not applicable

### d. Benefits and risks assessment, group relatedness

Patient burden is considered minimal

### e. Compensation for injury

There is no injury expected caused by study participation. Insurance exemption has been requested.

### f. Incentives (if applicable)

Not applicable

## 11. ADMINISTRATIVE ASPECTS, MONITORING AND PUBLICATION

### a. Handling and storage of data and documents

All participating hospitals have signed a data processing agreement with Luscii healthtech B.C. that complies with the general data protection regulations (GDPR) and national regulations (e.g. Algemene Verordening Gegevensbescherming (AVG)) that apply in the Netherlands. Moreover, all of the patients directly identifying personal data (e.g., name, address, etc.) will be separated from the research data (e.g., measurement data, etc.) and replaced by an assigned code. The directly identifying data will be only used to contact the patients and is only available to the investigators. The handling of personal data complies with the general data protection regulations (GDPR) and applicable national regulations (e.g. Algemene Verordening Gegevensbescherming (AVG)). For data collection and validation, an eCRF, including validation checks and appropriate user access rights, will be set up in CASTOR© ([www.castoredc.nl](http://www.castoredc.nl)). CASTOR© is a GCP compliant and meets the standard for information security management. All data will be stored in a secure place for 15 years after study end at OLVG Hospital. Electronic files will be archived on the OLVG 'SharePoint wetenschap anesthesiologie' server in a secure and controlled environment to maintain confidentiality. Electronic documents will be controlled with password protection according to best practices. Any data leaks that might occur regardless of these safety precautions will be reported to all parties within 1 working day after discovery of the leak.

### b. Monitoring and Quality Assurance

All medical specialists, nurses and other hospital personnel involved in perioperative care for surgical day care patients receive information an instruction about the study procedures either by an information letter (APPENDIX). The conduct of the study will be performed according to BROK/GCP standards and follow guidelines on improving and standardizing evaluations reports of web-based and mobile health interventions (33). Furthermore a clinical data management plan will be used with the objective of the clinical data management plan is to provide high-quality data by adopting standardized procedures to minimize the number of errors and missing data, and consequently, to generate an accurate database for analysis (APPENDIX). Accuracy and consistency checks will be carried out by way of validation, pre-specified and ad hoc checking by the researchers. A qualified monitor will be installed to perform study monitoring according to the monitoring plan. Monitoring will be performed to signal early aberrant patterns, issues with consistency, credibility, and other anomalies.

**c. Amendments**

Amendments are changes made to the research after a favourable opinion by the accredited METC has been given. All amendments will be notified to the METC that gave a favourable opinion. Non-substantial amendments will not be notified to the accredited METC and the competent authority but will be recorded and filed by the sponsor

**d. Annual progress report**

The sponsor/investigator will submit a summary of the progress of the trial to the accredited METC once a year. Information will be provided on the date of inclusion of the first subject, numbers of subjects included and numbers of subjects that have completed the trial, serious adverse events/ serious adverse reactions, other problems, and amendments.

**e. Temporary halt and (prematurely) end of study report**

The investigator/sponsor will notify the accredited METC of the end of the study within a period of 8 weeks. The end of the study is defined as the last patient's last follow-up. The sponsor will notify the METC immediately of a temporary halt of the study, including the reason of such an action. In case the study is ended prematurely, the sponsor will notify the accredited METC within 15 days, including the reasons for the premature termination. Within one year after the end of the study, the investigator/sponsor will submit a final study report with the results of the study, including any publications/abstracts of the study, to the accredited METC.

**f. Public disclosure and publication policy**

The study protocol will be registered before inclusion of the first patient on [www.clinicaltrials.gov](http://www.clinicaltrials.gov). The results of the study will find their way into (inter-) national scientific journals and guidelines. We will submit analyses to scientific journals in the field of anaesthesiology. A lay summary of the results will be published as well and send to the participants if they are interested.

